Informed consent will be sought for completion of the study eligibility screening and for participation in the study via oral and written consent respectively. Some patients may be incapable of providing informed consent. In such cases, informed consent will be obtained from their surrogate decision-maker. Surrogate decision-makers will be identified as the individual who is making decisions on behalf of the patient for clinical care in the ICU. Consent will be obtained in two steps. First, oral consent will be obtained to perform a brief (< 5 minute) in-bed assessment of muscle strength using a standardized protocol to determine eligibility. Only those patients who are weak, defined either by (a) composite muscle strength sum-score, using Medical Research Council (MRC) scale, <48/60, or (b) a handgrip strength of <11 kg in men and <7 kg in women(2), will be offered written informed consent (since demonstrated muscle weakness is an entry criteria). During the written informed consent process details on the intent of the proposed study, its design, the type of information collected, and potential risks and benefits of participation will be discussed. If surrogates were consented because of the patient's incapability, we will monitor the patient for return of capability and once they are capable, acquire consent from them for continuation in the study.

4-a-2) Planned flow of participants through the study

After consent is obtained, a chart review will be performed to ensure patient still meets eligibility and safety criteria (sections 5 and 4-f, respectively).

4-a-3) Randomization

After informed consent is obtained, eligible patients will be randomly assigned in a 2:1 ratio to the intervention (lorcaserin) or control group (placebo) respectively. (Please see Table 3 and section 4-a-6 for detailed study events.) Group assignment will be masked for patients, clinical and research staff administering the lorcaserin/placebo, and assessing outcomes (muscle strength, safety outcomes, or serum sample collection), as discussed under section 4-c.

4-a-4) Measurement of Exposures and Potential Confounders:

Patient exposures and potential confounders will be collected at study enrollment and are outlined in Table 1. Table 2 summarizes ICU-related exposures and possible confounders that will be collected during the study.

Table 1: Patient-related exposures and potential confounders – Baseline status

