4-a-6.11) Serum Drug Levels: Daily blood samples will be collected to determine lorcaserin serum levels by a LC-MS/MS assay and pharmacokinetics. The serum drug samples will be collected and run in at least 2 batches, with the first batch run on specimens after randomization of at least the first 3 patients to lorcaserin (will be done without unblinding the research team regarding the study ID of these subjects). The peak plasma concentration after oral dosing is 1.5 to 2 hours. However, feeding can increase the peak plasma time by 1 hour. Thus, peak concentration samples will be collected at 2hours \pm 15 minutes for NPO patients and at 3 hours \pm 15 minutes for fed patients. Lorcaserin has a plasma half-life of about 11 hours, and trough concentration samples will be collected at approximately two half-lives, or 24 hours \pm 30 minutes.

4-a-6.12) Electromyography (EMG) and Nerve Conduction Studies (NCS):

Nerve conduction will be assessed via the following screening nerve conduction studies in participants after enrolment, to detect potential peripheral neuropathy. NCS results will help us interpret the results of strength tests.

- Motor NCS of bilateral peroneal nerves
- Motor NCS of unilateral ulnar nerve. If ulnar neuropathy at the elbow is diagnosed (slowing of ulnar conduction velocity across the elbow to below 35 m/s or a drop in ulnar motor amplitude of >50% with stimulation above the elbow), Motor NCS of the ulnar nerve of the other extremity will be performed as well.

- Sensory NCS of unilateral ulnar and sural nerves

Motor unit recruitment rate will be assessed via the following EMG studies as well

- EMG of unilateral vastus lateralis muscle
- EMG of unilateral deltoid muscle

If EMG and NCS studies have already been done for clinical purposes, they will NOT be repeated for research purposes, and the pre-existing results will be used for research purposes.

4-b) Study duration and number of study visits required of research participants.

Each participant regardless of group, will be in the study for two 2-day blocks. The detailed timeline of events are detailed in Table 3.

4-c) Blinding, including justification for blinding or not blinding the trial, if applicable.

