All participants, clinical staff, and research staff (including those performing outcomes assessments and administering the drug/placebo) will be blinded to the randomization allocation. The investigational pharmacy (which will not be blinded) will prepare the lorcaserin/placebo for administration in similar forms and packaging to prevent unblinding.

If any unexpected, adverse event occurs that may be directly related to the study protocol, unblinding of treatment allocation for that specific participant will occur, as needed, for the principal investigator and IRB (the outcomes assessor(s) would still remain blinded if the patient continued in the trial). Time points and the number of 'unblinding' episodes will be recorded.

4-d) Justification of why participants will not receive routine care or will have current therapy stopped.

All participants, regardless of study group, will continue to receive routine medical care in the ICU. For safety reasons, in consultation with a panel of experts (Drs. [name] – Critical Care; [name] – Clinical Pharmacology; [name] – Psychiatry, [name] – MICU Pharmacist), the following procedures were developed and will be followed in the event a participant is scheduled to receive pharmacologic therapies that may potentially interact with the study drug (see Appendices A and B for list of drugs) to minimize the risk of serotonin syndrome or other potential adverse drug effect from CYP2D6 effect on drug metabolism.

1. First, a non-interacting substitute will be sought in consultation with the primary clinical team.
2. In the event that no safe and effective substitute is available, and the interacting agent is classified in
 - a. Appendix A, participants will be excluded or withdrawn from the study.
 - b. Appendix B participants will not receive more than one other serotonergic agent during the trial, with consideration of the following strategies when/if feasible
 - i. In consultation with the participant's clinical team, a decision will be made regarding the safety of temporarily discontinuing a non-essential drug therapy before the start of the 4-day protocol, and restarting the drug at least 2 days (i.e., 4 half-lives of lorcaserin) after the last administration of lorcaserin/placebo.

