 - ii. If the dosage of any interacting agent (e.g., analgesic) is routinely titrated for desired clinical effect, the clinical team will be informed and cautioned to ensure titration occurs with the consideration for potentiation or decrease in the interacting agent's effect.
 - iii. If neither substitution, temporary discontinuation or titration of a potential interacting agent is possible, the patient will be excluded / withdrawn from the study.

4-e) Justification for inclusion of a placebo or non-treatment group.

In our proposed study, patients will be randomized to receive either lorcaserin or Placebo. The FDA-approved drug under study in this trial, lorcaserin, does not have any published data supporting efficacy for muscle weakness in the ICU. Hence, no therapy known to be effective is being withheld from the placebo group. Given that our primary and secondary outcomes are based on semi-objective assessments of muscle strength or subjective assessments of cognitive/psychological symptoms, a control group (with blinded outcomes assessments) is required to reduce bias in patients' outcome assessment. Patients in the control group will continue with routine therapy as deemed appropriate by the clinical team.

4-f) Definition of treatment failure or participant removal criteria.

1. Participants will be removed from this study if the surrogate decision-maker, the patient (when capable of medical decision-making) or the patients' medical team makes a request for removal from the study.
2. As stated in Section 4-d, in the event a participant is scheduled to receive pharmacologic therapies that may potentially interact with the study drug (see appendix A), and substitution, gradual titration or discontinuation of interacting agent is not safe or feasible, within the decision rules outlined in Section 4-d, the participant will be withdrawn from the study.
3. The study drug or placebo will be discontinued for the following physiologic changes. Data collection will continue in these participants.
 1. An increase AST > 8 times the upper limit of normal (ULN)
 2. An increase in ALT > 8 times ULN,
 3. A decrease in creatinine clearance <30 mL/min,
 4. New-onset Q-T prolongation, defined as
 - QTc>500 msec
 - A >60 msec increase in QTc from baseline
 5. New-onset 2nd or 3rd degree heart block without a permanent pacemaker,
 6. Persistent heart rate <60 bpm
 7. New-onset priapism
 8. Serotonin Toxicity (as determined by Hunter Criteria, as previously described)

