- 2) replication of the primary analysis excluding any patients with neuropathy based on nerve conduction studies (29) within the intervention group,
- 3) comparison of the change from baseline to post-drug testing across the 10 mg versus 30 mg conditions using a paired t-test
- 4) a PK-PD analysis for all concentration-strength measures for all observations (across the 4 days) using a traditional Emax model pooling all subjects and all time points.

7-c) Statistical plan including sample size justification and interim data analysis.

The sample size (N=10 for lorcaserin and N=5 for placebo) is a convenience sample to establish preliminary data for a potential larger future study. With $\alpha = 0.05$, power = 80%, and a mean (standard deviation) baseline value of 9 (9) kg for the primary outcome of grip strength, under a 30 mg dose of lorcaserin we could detect a difference of >9 kg for the change in strength from baseline to post-drug testing (on the same day) for the intervention group versus no change for the placebo group. This difference represents a 100% increase in strength versus a 400% increase detected with an equivalent dose in the rat model. This calculation assumes that the baseline and post-drug testing measures would be highly correlated ($r = 0.8$). Under a worst case scenario (i.e., no correlation between baseline and post-drug testing), we could detect at least a 220% increase in strength which is adequate given the large increase expected based on rat models.

7-d) Early stopping rules

There are no early stopping rules for this pilot trial.

8) Risks

8-a). Medical risks, listing all procedures, their major and minor risks and expected frequency.

1) Side effects of Drug / Placebo:

Participants will be closely monitored for any side effects related to administration of the study drug or placebo.

The placebo has no known side effects.

Date: 1 August 2016

Principal Investigator: [name] PhD

Application Number: IRB00072940

The study drug, lorcaserin, has been extensively studied, has an excellent safety profile and is FDA approved for chronic use for purposes of weight loss(19). The major potential side-effects are listed below. A full list of side effects is available in Appendix C, the FDA prescribing information.

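### The first drug-level batch is triggered by a count of lorcaserin patients, so its timing could disclose allocation; the safeguard covers study IDs only

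*Combined protocol and SAP*

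**What the plan says.** Section 4-a-6.11 covers the lorcaserin serum assay. It plans two or more assay runs. The rule for the earliest of them is "the first batch run on specimens after randomization of at least the first 3 patients to lorcaserin". It adds that this "will be done without unblinding the research team regarding the study ID of these subjects".

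Section 4-c sets the blind: "All participants, clinical staff, and research staff (including those performing outcomes assessments and administering the drug/placebo) will be blinded to the randomization allocation". The one unblinded party it names is the pharmacy: "The investigational pharmacy (which will not be blinded) will prepare the lorcaserin/placebo". Section 4-a-3 also lists serum sample collection among the masked tasks.

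On allocation, 4-a-3 says that "eligible patients will be randomly assigned in a 2:1 ratio to the intervention (lorcaserin) or control group (placebo) respectively", and 7-c that "The sample size (N=10 for lorcaserin and N=5 for placebo) is a convenience sample". No randomisation method or block size is given. The protocol also does not say who calls for the batch, who learns that it has been run, who receives the results, or whether placebo samples are included.

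**The concern.** Blinded staff know how many patients have been randomised. They should not know how many of those are on lorcaserin. A batch that starts when the lorcaserin count reaches three links the two. Withholding study IDs does not break the link: if the batch is called when only three patients have been randomised, all three are on lorcaserin and no ID is needed.

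The blind matters here on the protocol's own argument. Section 4-e describes the strength outcomes as semi-objective and says that "a control group (with blinded outcomes assessments) is required to reduce bias in patients' outcome assessment". Under 8-c the principal investigator, who takes part in the daily conduct of the trial, decides whether expected ICU events count as associated with the protocol. With 15 patients planned, one to three known allocations is a material share.

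Nothing stated in the plan needs an arm-specific trigger. Section 7-d has no stopping rules, the PK-PD analysis in 7-b pools all observations, and no decision is tied to the first-batch result.

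**Working it through.** The plan gives no figure on this point, so there is none to reproduce.

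**Inputs.** Trigger: at least 3 patients randomised to lorcaserin (4-a-6.11). Ratio 2:1 (4-a-3). Arm sizes 10 and 5 (7-c). The randomisation method is not stated, so a range is shown. Steps 1 to 3 assume the worst case: the batch is called as soon as the third lorcaserin patient is randomised, and blinded staff see this.

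**Step 1. Probability that the first three patients are all on lorcaserin.**

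| Assumed scheme | Calculation | Result |
|---|---|---|
| Simple 2:1 | (2/3)³ | 29.6% |
| Fixed 10:5 list | (10×9×8)/(15×14×13) = 720/2730 | 26.4% |
| Blocks of 12 (8:4) | (8×7×6)/(12×11×10) = 336/1320 | 25.5% |
| Blocks of 9 (6:3) | (6×5×4)/(9×8×7) = 120/504 | 23.8% |
| Blocks of 6 (4:2) | (4×3×2)/(6×5×4) = 24/120 | 20.0% |
| Blocks of 3 (2:1) | impossible | 0% |

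**Step 2. What a later prompt trigger reveals.** If the batch is called at patient n, patient n is on lorcaserin with certainty, and exactly two of the n−1 earlier patients are.

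- At n = 4 each earlier patient has probability 2/3, which is the 2:1 prior. Only patient 4 is identified. The trigger falls here with probability 29.6% (simple), 33.0% (10:5 list), 40% (blocks of 6) or 66.7% (blocks of 3).
- At n = 5 each of the four earlier patients drops to 2/4 = 50% under a 10:5 list, simple randomisation or blocks of 6. With blocks of 3 (trigger at n = 5 in 33.3% of cases), patient 4 must be on placebo, if the block size is known.

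**Step 3. Effect on the next patient, after three known lorcaserin patients.** Under a 10:5 list, 7 of the 12 remaining places are lorcaserin, so the probability falls from 67% to 7/12 = 58%. Within a block of 6, one of three places remains: 33%. Under simple randomisation it stays at 67%.

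**Step 4. A trigger on total numbers.** Summing over the patient at which the third lorcaserin allocation falls gives the probability that a batch of fixed size holds at least three:

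- 6 patients: 0.2637 + 0.3297 + 0.2398 + 0.1199 = 95% (10:5 list); 0.2963 + 0.2963 + 0.1975 + 0.1097 = 90% (simple).
- 8 patients: 100% (10:5 list, since at most 5 are on placebo); 0.8998 + 0.0549 + 0.0256 = 98% (simple).

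The third lorcaserin patient is expected at patient 3×16/11 = 4.4 (10:5 list) or 3/(2/3) = 4.5 (simple).

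**The case against.** The leak needs two conditions that the protocol does not state: that the batch is run promptly, and that blinded staff learn when. Three lorcaserin patients is a minimum, so a later batch is allowed, and a late one says little; after 8 patients on a 10:5 list, everyone already knows that at least three are on lorcaserin. The same sentence commits to protecting the identity of these patients, and an unblinded pharmacy exists that could manage the timing. All of this stands. It makes the leak possible rather than certain, and the percentages upper limits. It does not remove the gap, because nothing tells the person calling the batch to wait or to conceal when it is run.

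A reader might infer that the most recently randomised patient would be unmasked before the Day 3 handgrip test, because the trigger is worded as randomisation. That goes too far. The batch is run on specimens, and Table 3 schedules samples through Day 4. If complete sets are required, that patient's Day 3 test is already done.

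A reader might also add the chances of a trigger at patient 3 or 4 (about 59% under simple randomisation or a 10:5 list) and treat the total as the size of the breach. Step 2 shows why not: at patient 4 one patient is identified, and nothing new is learnt about each of the other three.

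**Conclusion.** The concern holds in a conditional form. The trigger depends on an arm-specific count and the safeguard protects IDs but not timing, so a prompt and visible first batch can disclose allocation. In that case the triggering patient is identified under every scheme, and the first three patients are all identified with probability between 0% (blocks of 3) and 29.6% (simple 2:1).

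The documents do not support saying that the blind will be broken, that 20% is a lower bound on identifying the first three, or that the primary outcome of the triggering patient is compromised. If full specimen sets are required, the remaining harm is mainly to the investigator's judgements about relatedness and to the masking of later allocations, where the shift for the next patient runs from none (simple) through 67% to 58% (10:5 list) to 67% to 33% (block of 6).

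This is an incomplete safeguard in a small pilot, not disregard for the blind. It still merits a change, because a rule without the leak is available and no stated decision depends on the early result.

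**What to change.** In 4-a-6.11, replace the arm-specific trigger with a prespecified total number of patients who have completed Day 4, regardless of arm. Six completers give at least three on lorcaserin with probability about 95% (10:5 list) or 90% (simple 2:1); eight give 100% or 98%. The 100% relies on no more than 5 placebo patients among the completers, which should be checked against the replacement rule in 4-f. State that all patients' samples in the batch are assayed, placebo included, and that results go only to unblinded staff until database lock.

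The change is a sentence or two and adds no samples. The price is a later first assay: the present rule would be met at about patient 4.4 on average, while eight completers falls past the midpoint of a 15-patient trial. Six is a reasonable compromise if early assay data matter, with a small chance that the batch holds fewer than three lorcaserin patients. If the arm-specific trigger is kept, the section should at least say that only unblinded staff know when the batch is run and what it shows.

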Below, we propose a sequential 2-level dose escalation study of the safety, pharmacokinetics (drug concentration over time) and pharmacodynamics (i.e., muscle strength response) of lorcaserin in critically ill patients with muscle weakness. We selected two different one-time doses of the study drug to provide dose-response data over a range of doses deemed safe for the ICU setting. As described above, these doses are anticipated to bracket (i.e., fall above and below) the anticipated effective dose based on preclinical studies and established differences between species. Observations for drug effect on muscle weakness, adverse events, and drug concentration will be made at specified intervals after each dose (as outlined below). The time between doses, 48 hours, was selected to provide time for the anticipated drug concentrations and muscle strength effects to return to baseline before the second, higher dose

4) Study Procedures

4-a) Study design, including the sequence and timing of study procedures (distinguish research procedures from those that are part of routine care).

Potentially eligible participants will be identified through screening of the Johns Hopkins Hospital's medical and surgical ICU census (see section 5 for specific eligibility criteria) and IRB approved medical floors under a HIPAA waiver. We will be engaging the CCDA to develop and provide us a daily report of patients on our IRB approved floors who were screened by a treating provider for sepsis and the results of this sepsis screen. Daily reports would be sent to the SAFE virtual desktop. Members of research team who are on this protocol will then review the charts of these patients who had a positive sepsis screen to determine if they meet other inclusion criteria and do not meet exclusion criteria. Potential eligibility will be confirmed by the research team with the patient's attending physician. A treating provider will obtain permission from the patient or surrogate to approach them for a discussion about possible participation in the study.

4-a-1) Informed Consent

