Patient Risk Factors	Method for data collection	Measurement Scale
Age/sex/race/ethnicity	Chart review	Continuous/Binary/Categorical
Weight/Height	Chart review	Continuous
Comorbidities: Charlson* & Functional Indices**	Chart review	Ordinal
Severity of illness: APACHE II***	Chart review	Continuous
Leg/Hand dominance	Patient/Proxy interview	Binary
Past Psychiatric History***	Chart review	Categorical

*Charlson Comorbidity index: a score derived from 19 categories of comorbidities, with an increased score reflecting an increased likelihood of one-year mortality(20).

**Functional Comorbidity Index: An 18 item list of diagnoses which uses physical function as the outcome of interest, with increased score indicative of decreased function(21).

Date: 1 August 2016

Principal Investigator: [name] PhD

Application Number: IRB00072940

****Acute Physiology and Chronic Health Evaluation (APACHE II): An index of disease severity that takes into account age, pre-existing medical conditions, and 12 acute physiologic variables that are assessed during the first 24 hours of ICU admission. Scored on a scale from 0-71, with higher scores indicating more severe disease and increased mortality risk(22).*

Table 2: Potential confounders – ICU status

ICU exposure risk factors	Method of Data Collection	Measurement Scale
Sequential Organ Failure Assessment (SOFA) Score**	Chart review	Continuous
ICU admission diagnosis details	Chart review	Categorical

** *SOFA: A composite score that takes into account 6 organ systems used to assess the severity of organ dysfunction in ICU(23), collected on Days 1 and 3.*

4-a-5) Sequence and Timing of Study Events

On Day 1, intervention and control group participants receive 10 mg of lorcaserin or placebo, respectively. Both groups also will undergo assessments before and after administration of lorcaserin/placebo (for assessment details and times, see table 3 and section 4-a-6)

On Day 2, the intervention and control group participants will not receive any lorcaserin/placebo, but will undergo repeat assessments (for assessment details and times, see table 3 and section 4-a-6)

On Day 3, the intervention and control group participants receive 30 mg of lorcaserin or placebo, respectively. Both groups also will undergo assessments before and after administration of lorcaserin/placebo (identical to Day 1).

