‡ Peak concentration serum samples will be collected 2 hours ± 15 minutes or 3 hours ± 15 minutes after drug administration (see section 4-a-6.11 for details) and trough concentration serum samples will be collected 24 hour ± 30 minutes after drug administration (see section 4-a-6.11 for details)

† Days 2 and 4 are consecutive to days 1 and 3 respectively.

‡ Day 3 may or may not be consecutive to day 2 depending on assessor availability.

Safety Measures

4-a-6.1) *Chart Review*: A daily review of participants' medical records for interim medical history and medications will be performed to monitor for any safety issues and ensure that participants continue to meet eligibility and safety criteria (see sections 5 and 4-f respectively).

4-a-6.2) *Laboratory Tests*: As indicated in table 3 above, participants will undergo daily blood draws for the following standard laboratory tests: Heme 8 and CMP. In particular, laboratory tests will be obtained prior to every dose of lorcaserin or placebo to ensure that patients meet eligibility and safety criteria (see sections 5 and 4-f respectively). If the relevant tests have already been done for clinical purposes, they will NOT be repeated for research purposes. As these labs are typically measured, at least daily, in the ICU setting, they may not need to be drawn for research purposes and the pre-existing values will be reviewed for research purposes.

4-a-6.3) *EKG*: Daily EKGs will be obtained to determine if participants develop bradycardia, new-onset QT prolongation (as defined in Section 4.f.3.4 below) or new 2nd or 3rd degree AV block. In particular, this test will be obtained prior to every dose of lorcaserin or placebo to ensure that patients meet eligibility and safety criteria (see sections 5 and 4-f respectively). If this test has already been done for clinical purposes, it will NOT be repeated for research purposes. As this test is commonly done, at least daily, in the ICU setting, it may not need to be done for research purposes and the pre-existing test will be reviewed for research purposes.

Date: 1 August 2016

Principal Investigator: [name] PhD

Application Number: IRB00072940

4-a-6.4) Richmond Agitation Sedation Scale (RASS)(25): is a validated instrument to measure agitation and sedation status in ICU patients. Participants will be screened for their sedation status daily as well as pre- and post-drug or placebo administration as indicated in table 3 above.

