5) Chart Abstraction: There is a risk of loss of privacy, since we will be collected data on participants.

6) Strength testing: Participants may feel some tiredness or discomfort in the arm and leg muscles

7) Questions: There is a small chance that a participant could become uncomfortable, bored or fatigued in answering our questions.

8-b) Steps taken to minimize the risks.

1) Side effects of drug/placebo

a) Serotonin Syndrome and NMS-like reactions:

Although this syndrome is rare, the theoretical risk of serotonin syndrome and NMS-like reactions will be mitigated by

- i. Monitoring participants for liver and renal failure, which may affect drug levels
- ii. Reviewing medication lists to exclude patients on drugs that may cause serotonin syndrome when administered along with lorcaserin (see Appendix A and section 4-d above).
- iii. Allowing participants to be on no more than 1 serotonergic agent (plus lorcaserin/placebo) during the trial.
- iv. Closely monitoring patients, for toxicity using the NPI-C for mental status changes and Hunter Criteria for Serotonin toxicity.

b) Cardiac valvular and conduction abnormalities:

Patients with a history of valvular heart disease, bradycardia, and 2nd or 3rd degree AV block without pacemaker will be excluded. Participants are unlikely to develop new onset valvular defects given that they will only receive two doses in this trial. Participants will be closely monitored via EKG for bradycardia and new onset 2nd or 3rd degree AV block.

c) Cognitive impairment, Psychiatric Disorders (including euphoria and dissociation) and Depression:

Patients with pre-existing cognitive impairment and psychosis will be excluded. During the trial, patients will be closely monitored using the RASS, CAM-ICU and NPS (Neuropsychiatric screening) instruments.

d) Hypoglycemia: Patients will be excluded if they are receiving a sulfonylurea medication at the time of the study

e) Priapism: this is a theoretical risk will be mitigated by excluding patients with a prior history of priapism, and monitoring during the trial via any noted side effect.

2) Risks of stopping/adjusting other medications: These risks will be assessed on a case-by-case basis, in consultation with the participants' medical team.

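### Scheduled safety observation stops about 24 h after the 30 mg dose, although the protocol itself works with 48 h for lorcaserin to clear

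*Combined protocol and SAP*

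**What the plan says.** Three passages bear on how long lorcaserin matters after a dose.

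- **Section 3-f (design rationale):** "The time between doses, 48 hours, was selected to provide time for the anticipated drug concentrations and muscle strength effects to return to baseline".
- **Section 4-d, item 2.b.i:** a non-essential interacting drug may be paused for the study, with "restarting the drug at least 2 days (i.e., 4 half-lives of lorcaserin) after the last administration of lorcaserin/placebo".
- **Section 4-a-6.11 (serum levels):** "Lorcaserin has a plasma half-life of about 11 hours, and trough concentration samples will be collected at approximately two half-lives", at 24 h ± 30 minutes.

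The schedule is in sections 4-a-5 and 4-b and in Table 3. The 10 mg dose is given on Day 1. For the higher dose: "On Day 3, the intervention and control group participants receive 30 mg of lorcaserin or placebo, respectively". The Table 3 footnotes add that "Days 2 and 4 are consecutive to days 1 and 3 respectively", and that Day 3 may be later than the day after Day 2. Section 4-b states: "Each participant regardless of group, will be in the study for two 2-day blocks". Table 3 has no column after Day 4, and no section gives a collection period for adverse events.

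On concurrent drugs, section 8-b lists among its safeguards: "Allowing participants to be on no more than 1 serotonergic agent (plus lorcaserin/placebo) during the trial". Section 4-d has a matching limit for Appendix B drugs.

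**The concern.** Safety is the first objective (2-1), and 30 mg is the dose in the primary analysis (7-a). By the protocol's own figures the drug is still clearing when the last scheduled check is made after that dose. The interval from 24 to 48 h has a scheduled look at its end after 10 mg and none after 30 mg. With 10 patients planned on lorcaserin, a single event missed in that interval would change the safety description noticeably.

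The drug-interaction safeguards raise a related question. The restart rule runs past Day 4, but only for a drug that was paused. The documents do not say whether the limit on serotonergic agents continues past Day 4, or whether it reaches an Appendix A or B drug started for the first time after the last visit. The case is realistic: every participant has known or suspected infection, and the antibiotic linezolid is on Appendix A.

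**Working it through.** **Inputs.** Half-life 11 h (4-a-6.11). Restart delay 48 h, described as 4 half-lives (4-d). Dose interval 48 h (3-f). Doses 10 mg on Day 1 and 30 mg on Day 3 (4-a-5). Last scheduled safety measures on Day 4, where the only timed item is the trough sample at 24 h ± 30 minutes (Table 3 footnotes).

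**Step 1: the protocol's own figures.** Half-lives elapsed = hours / 11.
- 48 / 11 = 4.36, stated as 4 (4 × 11 = 44 h).
- 24 / 11 = 2.18, stated as about 2.

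Both reproduce with rounding, and both are exact at a 12 h half-life.

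**Step 2: amount remaining.** Assuming first-order elimination and counting time from the dose, the fraction remaining is 0.5^(t / half-life).

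| Time after dose | Fraction, 11 h | After 10 mg | After 30 mg |
|---|---|---|---|
| 24 h | 0.220 | 2.2 mg | 6.6 mg |
| 44 h | 0.0625 | 0.6 mg | 1.9 mg |
| 48 h | 0.049 | 0.5 mg | 1.5 mg |

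Over 23.5 to 24.5 h the fraction is 0.23 to 0.21; at a 12 h half-life it is 0.25 at 24 h. If the half-life in these patients were 16.5 or 22 h (assumed; the documents give no such figure), the fraction at 24 h would be 0.365 or 0.469, that is 10.9 or 14.1 mg after 30 mg.

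**Step 3: which measures reach about 48 h after 10 mg.**
- Laboratory tests and EKG must precede every dose (4-a-6.2, 4-a-6.3), so both are seen before the Day 3 dose.
- RASS and CAM-ICU are done twice on Day 3, the first time within 4 h of dosing. With doses 48 h apart, that is 44 to 48 h after 10 mg.
- The Hunter criteria and the neuropsychiatric screen are listed once on Day 3, with no time relative to the dose. A look at 48 h after 10 mg cannot be shown for them.

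No measure is scheduled beyond about 24 h after 30 mg.

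**Step 4: ratio of elapsed times to the last look.** For the four measures in the first two bullets it is 24 / 48 = 0.50. If Day 3 were delayed so that the gap became 72 or 96 h (assumed), it would be 0.33 or 0.25, but Table 3 schedules nothing on the extra days.

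**Step 5: the drug restrictions side by side.** The limit on serotonergic agents applies while the trial runs (4-d, 8-b). Participation is two 2-day blocks (4-b), and 4-d itself speaks of a 4-day protocol. Together these suggest that the limit ends on Day 4, but no passage says so. The restart rule holds paused drugs off for at least 48 h after the last dose. No passage addresses a drug first started after Day 4.

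**The case against.** The strongest reply is that the design treats the doses alike. Each has a two-day block, Day 4 repeats Day 2, and both arms follow one schedule. Exposure is highest a few hours after dosing, when RASS and CAM-ICU are repeated, and is falling throughout the uncovered interval. By the same decay formula, the weight-loss regimen of 10 mg twice daily (12 h apart) has a steady-state trough of 10 × 0.4695 / (1 − 0.4695) = 8.8 mg, so 6.6 mg at 24 h is below the lowest level of that regimen. Severe renal insufficiency and acute liver failure are excluded, which limits the case for long half-lives. Section 8-c requires serious study-related events to be recorded and reported, with no Day 4 cutoff. Consent is entered in the medical record so that ICU staff know of participation, and the investigator is involved daily.

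Much of this stands, and it rules out several readings a reader might infer:

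- **That 30 mg gets half the observation window overall.** This depends on crediting the checks before the Day 3 dose to the 10 mg dose. It is fair for laboratory tests, EKG, RASS and CAM-ICU, but not shown for the Hunter criteria or neuropsychiatric screen. The ratio is exact only at a 48 h gap.
- **That the limit on serotonergic agents lapses on Day 4.** This is an inference from sections 4-b and 4-d, not a stated rule.
- **That a planned safety comparison of the two doses is compromised.** Sections 7-a and 7-b plan comparisons of strength only.
- **That observation is missing when exposure peaks.** The gap lies in the tail.

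What the reply does not remove is the mismatch between the 48 h figure and the 24 h stop. Reporting under 8-c is also no substitute for scheduled collection: agitation and delirium are among the anticipated ICU events there, reportable only if the investigator links them to the study protocol.

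**Conclusion.** The point holds as a shortfall in systematic safety data. Scheduled observation ends 2.2 half-lives after the higher dose, with about 22% remaining, while the protocol's clearance allowance of 48 h corresponds to about 5%. These percentages rest on the stated half-life and on first-order elimination. The statement that observation ends at about 24 h rests on the Day 4 trough time, since the other Day 4 measures carry no clock time.

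The comparison of lorcaserin with placebo is not biased, and the strength analyses are unaffected. The restriction passages show an unaddressed case rather than a contradiction: the restart rule and the limit on concurrent agents cover different things, and newly started drugs fall between them. Severity is low to moderate: a cheap improvement to a 15-patient pilot, not a flaw that undermines it.

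**What to change.** 1. Add one chart review about 48 h after the Day 3 dose in both arms, covering adverse events, new medications, and any EKG or laboratory results available from clinical care.
2. Tabulate adverse events by arm over the same 48 h after each dose. State this window in the protocol, and keep it at 48 h for the 10 mg dose when Day 3 is delayed.
3. State when on Day 3 the Hunter criteria and neuropsychiatric screen are done relative to the dose, so that their coverage is known.
4. Reconcile the limits on serotonergic agents (4-d, 8-b), the length of participation (4-b) and the restart rule (4-d). State when the limits end and whether newly started Appendix A or B drugs are covered. The period is for the investigators and clinical pharmacology to set; none is proposed here.

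The cost is 15 extra chart reviews and a wording amendment, with no new procedure or blood draw. Depending on how item 4 is settled, oversight of interacting drugs may last up to a day longer.
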